4.8.1 Exposure to Study Medication

The number and percentage of patients who received obinutuzumab will be summarized by treatment course, along with summary statistics for the dose of obinutuzumab received at each infusion and overall, and the duration of exposure. Duration of exposure will be calculated as:

$$\text{exposure date (as defined in Section 4.2)} - \text{date of first infusion} + 1.$$

Obinutuzumab exposure data will be determined using the dosing information as recorded on the obinutuzumab administration log on the eCRF and the actual treatment received as per IxRS. Exposure to obinutuzumab will not include obinutuzumab given as rescue, which will be analyzed separately.

Exposure to MMF will be summarized using the average daily dose, total cumulative dose, and treatment duration. Treatment duration will be calculated as:

$$\text{date of last dose} - \text{date of first dose} + 1$$

The total cumulative dose will be calculated by summing the total daily dose over the treatment duration. Average daily dose will be calculated as:

$$\text{total cumulative dose} \div \text{treatment duration}$$

MMF exposure data will be determined using the dosing information as recorded on the MMF administration log on the eCRF and the actual treatment received as per IxRS. Exposure to MMF will not include MMF given as rescue, which will be analyzed separately.

Exposure to corticosteroids will be summarized using the average daily dose, total cumulative dose, and treatment duration. Treatment duration will be calculated as:

$$\text{date of last dose} - \text{date of first dose} + 1$$

The total cumulative dose will be calculated by summing the total daily dose over the treatment duration. Average daily dose will be calculated as:

$$\text{total cumulative dose} \div \text{treatment duration}$$

Corticosteroid exposure data will be determined using the dosing information as recorded on the concomitant medication administration log on the eCRF and the actual treatment received as per IxRS. Exposure to corticosteroid will not include corticosteroid given as rescue, which will be analyzed separately.

4.8.2 Adverse Events

Adverse events will be mapped and reported using the Medical Dictionary for Regulatory Activities (MedDRA) thesaurus using the most current version at the time of analysis (Version 20.1 or later). Glossaries showing the mapping of investigator verbatim terms to coded events will be produced.

Treatment-emergent adverse events (TEAEs) will be summarized. All AEs referenced in the section below will be TEAEs. TEAEs are defined as those AEs with observed or imputed onset date on or after the start date of trial treatment. Only where the most extreme intensity is greater than the initial intensity (or if most extreme intensity is not missing and initial intensity is missing) will events with an onset date prior to the start of trial treatment be considered treatment-emergent. An AE with a completely missing start date will be assumed to be treatment-emergent unless the AE has a complete non-imputed end date that is prior to study Day 1.

Listings will show all AEs reported, including AEs occurring after rescue therapy, and any AEs that may have occurred during the oral corticosteroid dose adjustments in the screening period.

AEs will be summarized by system organ class (SOC) and preferred term (PT), and will be presented in order of descending frequency summed across the treatment arms within each SOC and PT.

The following will be summarized, and/or listings produced where required:

- All AEs
- Serious Adverse Events (SAEs)
- AEs by relationship to obinutuzumab/placebo
- AEs by relationship to MMF/MPA
- Corticosteroid-related adverse events
- AEs leading to study drug dose modification or interruption
- AEs by common terminology criteria grade
- Infections
- Serious Infections
- Infusion related reactions (IRRs)
- Serious IRRs

Obinutuzumab—F. Hoffmann-La Roche Ltd

Statistical Analysis Plan

WA29748

- AEs leading to withdrawal
- AEs leading to death

AEs to monitor will be listed, including:

- Opportunistic infections (Roche Standard AE Grouped Term [AEGT] Basket)

AE rates per 100 patient-years exposure will be produced for key safety events. Rates will be based on all occurrences of AE. AE rate per 100 patient-years is defined as:

$$(\text{number of events} \div \text{total exposure}) \times 100$$

The 95% confidence intervals (CIs) will be calculated based on exact poisson distribution.

Positive pregnancy results will be listed, as identified using the serum test results.

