### **5.3.5.4 Persistent or Recurrent Adverse Events**

A persistent adverse event is one that extends continuously, without resolution, between patient evaluation time points. Such events should only be recorded once on the Adverse Event eCRF. The initial severity (intensity or grade) of the event will be recorded at the time the event is first reported. If a persistent adverse event becomes more severe, the most extreme severity should also be recorded on the Adverse Event eCRF. Details regarding any increases (or decreases) in severity will be captured on the Adverse Event Intensity or Grade Changes eCRF. If the event becomes serious, it should be reported to the Sponsor immediately (i.e., no more than 24 hours after learning that the event became serious; see Section 5.4.2 for reporting instructions). The Adverse Event eCRF should be updated by changing the event from "non-serious" to "serious," providing the date that the event became serious, and completing all data fields related to serious adverse events.

A recurrent adverse event is one that resolves between patient evaluation time points and subsequently recurs. Each recurrence of an adverse event should be recorded as a separate event on the Adverse Event eCRF.

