4.2 ANALYSIS OF STUDY CONDUCT

Analyses of study conduct will be carried out on the safety population or all randomized patients, as appropriate.

A summary of enrollment by investigator site will be produced.

The number of patients who completed or discontinued from the study including the reason for discontinuation, will be summarized by treatment group. A listing of early discontinuations will be produced.

Major protocol deviations will be listed. Any study conduct that is impacted by COVID-19 or Ukraine-Russia conflict will be summarized in the final CSR.

Patient duration in the entire study will be summarized. Duration will be calculated as:

$$\text{date of last visit} - \text{date of the first dose} + 1$$

Previous and concomitant medications will be summarized descriptively by mapped term and treatment group. A summary of rescue medications will also be produced.

A summary of the number of patients who experience treatment failure along with the reason(s) for treatment failure will be produced. The number of patients receiving rescue will also be listed and summarised.

A summary of exposure to study treatment will be produced using the dose recorded on the electronic case report form (eCRF). The number of obinutuzumab/placebo infusions and dose received at each infusion and overall will be summarised by treatment group. The total cumulative dose of obinutuzumab/placebo over the 52-week treatment period will be summarised. Note that these summaries highlight adherence to the blinded study treatment and not exposure to the active treatments (which will be described separately). Proportion of patients received rescue medication will be summarized by treatment group.

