4.6.1.5 Treatment Failure

Treatment failure occurs in the following scenarios:

- Patients who do not exhibit a response to the initial 2-week course of increased corticosteroids for treatment of renal flares and who initiate a new immunosuppressive therapy.
- If patients require a new immunosuppressive drug (other than corticosteroids) for treatment of their extrarenal SLE flare, those patients will be counted as treatment failures and will not receive further study drug but will continue their protocol mandated study visits.
- Any patient who switches to rescue medication will be considered a non-responder.

The clinical definitions of treatment failure above are aligned with “non-responder” classification for the primary analysis. Patients experiencing treatment failure will be categorized as non-responders in the primary analysis but will continue to be followed in the study per the schedule of assessments. Patients who achieve complete renal

response without experiencing an event constituting treatment failure beforehand will not be categorized as non-responders, regardless of whether they subsequently meet the criteria.

Patients who experience treatment failure are eligible to receive rescue therapy during the treatment period as per the investigator's best medical judgment. Patients who receive rescue therapy will continue to be followed in the study per the schedule of assessments.

Patients who receive rescue therapy for LN will be evaluated up to the point of rescue only for all main efficacy analyses. Methods for data handling and/or imputing post-rescue data are described throughout Section 4.6.1. Additional exploratory summaries on key efficacy assessments will be produced that will include rescue data. Safety analyses will include data up to the point of rescue. Cumulative safety analyses will be presented for safety summaries separately.

Listings will be provided for all data, including post rescue safety data.

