4.8 SAFETY ANALYSES

The safety analysis will be performed on the safety population as defined in Section 4.1.3. Analyses of safety data will include patients up to the point of receipt of non-corticosteroid rescue only. All safety data including the post-rescue data will be summarized separately for key safety outputs.

All safety outputs will include cumulative data to the final database lock. In addition, data collected after Week 104 will be summarized separately for key safety outputs to understand the Safety events occurring during the B-cell follow-up period only. Safety data will be summarized by treatment groups.

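### Adverse event rates count every recurrence but carry exact Poisson 95% limits, which are too narrow for frequent recurrent events if patients differ in risk

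*SAP*

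**What the plan says.** SAP 4.8.2 plans event rates in addition to the usual patient-level tables: "AE rates per 100 patient-years exposure will be produced for key safety events". The numerator is explicit: "Rates will be based on all occurrences of AE". The rate is the number of events divided by total exposure, times 100. The interval method is equally explicit: "The 95% confidence intervals (CIs) will be calculated based on exact poisson distribution". No robust, negative binomial or first-event alternative is named.

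Protocol 5.3.5.4 fixes how repeats enter the database: "Each recurrence of an adverse event should be recorded as a separate event on the Adverse Event eCRF". An event that resolves and returns therefore adds to the count each time.

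Three details around the rate are left open. The SAP does not list its key safety events. It does not define total exposure. For obinutuzumab exposure duration, SAP 4.8.1 refers to an exposure date in Section 4.2, but that section contains none; it gives only time in study, from first dose to last visit ("Patient duration in the entire study will be summarized").

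**The concern.** An exact Poisson interval assumes that the variance of the total count equals its mean. That holds if every patient has the same underlying rate and events within a patient are independent. It fails if some patients are prone to repeated events and others are not. The total then varies more from sample to sample than the Poisson formula allows, and the excess grows with the expected number of events per patient.

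The SAP does not say which events will be rated. SAP 2.2.4 names infections and infusion reactions among the events of special interest, and SAP 4.8.2 tabulates both separately. It is a reasonable inference, though no more than that, that an event able to recur over two years is on the list. If so, its interval in each arm will look more precise than the data allow, and a reader comparing arms by eye may see a clearer separation, or a clearer similarity, than is justified.

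**Working it through.** The documents state no event rate, count or dispersion, so there is no figure of the plan's own to reproduce. The check asks how the stated method behaves over a range of assumed values.

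**Inputs**
- 60 patients per arm (SAP 2.3; planned number).
- 104 weeks of follow-up, taken as 2 years, so 120 PY per arm (Protocol 3.1 follows patients to at least Week 104).
- Assumed: event rates of 2 to 100 per 100 PY.
- Assumed: patient risks follow a gamma distribution with mean 1 and variance k = 0, 0.5, 1 or 2.

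**Variance inflation.** With m expected events per patient, the true standard error of the total divided by the Poisson standard error is √(1 + k·m). At 50 per 100 PY, m = 0.5 × 2 = 1, so the ratio is √1.5 = 1.22, √2 = 1.41 and √3 = 1.73 for k = 0.5, 1 and 2. At 10 per 100 PY, m = 0.2 and the ratios are only 1.05, 1.10 and 1.18.

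**Coverage of the exact Poisson interval.** For D events the limits are χ²(0.025; 2D)/2 and χ²(0.975; 2D+2)/2, divided by person-time. Simulated coverage (20,000 runs per setting):

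| Rate per 100 PY | k = 0 | k = 0.5 | k = 1 | k = 2 |
|---|---|---|---|---|
| 10 | 96% | 95% | 94% | 92% |
| 25 | 96% | 93% | 90% | 85% |
| 50 | 96% | 91% | 86% | 77% |
| 100 | 96% | 84% | 76% | 63% |

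At 5 per 100 PY coverage is 94–96% for every k tried, and at 2 it is 98–99%. Unequal follow-up changes little: if 20% of patients leave uniformly over the two years, coverage at 50 per 100 PY is 91/85/77%.

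**A worked example.** Take 60 events in 120 PY, a rate of 50 per 100 PY.
- Exact Poisson: 38.2 to 64.4.
- Patient-level, on the log scale: SE = √((1 + k·1)/60), which at k = 1 is 0.183. With t(59 df) = 2.001, 50 × exp(±2.001 × 0.183) = 34.7 to 72.0.

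**The alternative.** For patient i with yᵢ events and person-time tᵢ, and arm rate r = D/Σtᵢ, the robust variance of log r is [n/(n−1)] × Σ(yᵢ − r·tᵢ)² / D². The interval is r × exp(±t(n−1)·SE). If an arm has no events, exact Poisson limits are used for it. In the same simulations this rule covers 96–97% at 2 and 5 per 100 PY and 94–95% at 10 to 100, for k = 0 to 2. The fallback is needed in 9–10% of runs at 2 per 100 PY, in under 0.5% at 5, and practically never above that.

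**Width relative to exact Poisson (median)**

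| Rate per 100 PY | k = 0 | k = 0.5 | k = 1 | k = 2 |
|---|---|---|---|---|
| 10 | 0.97 | 1.02 | 1.06 | 1.13 |
| 50 | 0.99 | 1.20 | 1.38 | 1.68 |
| 100 | about 1.00 | 1.40 | 1.70 | 2.18 |

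At 2 per 100 PY the ratio is about 1.09 whatever k is, among runs with at least one event.

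**The case against.** The case against giving this much weight is fair in several respects. The shortfall needs a frequent event on a list the SAP does not give, and between-patient variation that no document quantifies. At 10 per 100 PY the loss is small; it becomes material from about 25 to 50 per 100 PY with k of 1 or more. The rates are descriptive: no test or stopping rule uses them, and Protocol 6.5.1 also plans numbers and percentages of patients with events. Week 52 and Week 104 reports already exist (SAP Section 1), so a new method could break comparability if those reports used exact Poisson, which the documents do not show. All of this limits the size of the point. It does not make a Poisson interval suitable for clustered counts.

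A reader might go further and infer that the rates themselves will be understated, because rescued patients stay in follow-up ("Patients who receive rescue therapy will continue to be followed in the study per the schedule of assessments") and time in study runs to the last visit. The documents do not support that. SAP 4.8 says: "Analyses of safety data will include patients up to the point of receipt of non-corticosteroid rescue only". The natural reading cuts a patient's events and time together, and nothing says that time continues after events stop being counted.

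A reader might likewise infer that B-cell follow-up time dilutes the rates. SAP 4.8 does make the safety outputs cumulative to database lock, but it also summarizes data after Week 104 separately for key outputs, and Protocol Appendix 2 schedules adverse event collection at those visits. The undefined terms and the unresolved reference are missing detail, not evidence of bias.

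**Conclusion.** The point holds for the interval method. Counting all occurrences while using exact Poisson limits gives intervals that are too narrow for frequent recurrent events if patients differ in risk. In the illustration, a nominal 95% interval covers about 91/86/77% at 50 per 100 PY and 84/76/63% at 100, for k = 0.5/1/2. These figures rest on the planned arm size, two years of follow-up, gamma-distributed risks, and assumed rates and k.

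It would be wrong to conclude that all the planned intervals are unsound: for rare events, or with equal risks, exact Poisson is adequate. Nor does anything here touch the primary analysis. This is a low-severity improvement to descriptive safety reporting.

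**What to change.** In SAP 4.8.2, replace the exact Poisson sentence with one rule for every rated event in both arms: a patient-level robust (sandwich) 95% interval on the log rate, with log person-time as offset and a t quantile on n−1 degrees of freedom. Where an arm has no events, show exact Poisson limits for it and flag them. Events need not be sorted by expected frequency. That also avoids choosing a method event by event when two reports have already been issued. If the Week 52 and Week 104 reports used exact Poisson, those limits can be kept alongside for comparability.

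In the same edit, list the key safety events; state that person-time starts, stops and is cut at non-corticosteroid rescue exactly as event counting is; and correct the 4.8.1 reference to Section 4.2.

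The cost is SAP wording and minor programming. For k = 0.5 to 2, intervals for frequent events widen by about 1.2–1.7 times at 50 per 100 PY and 1.4–2.2 times at 100. Without clustering, widths hardly change at 5–100 per 100 PY and grow by about 1.09 times at 2.

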#### **4.3.2.2 Mycophenolate Mofetil/Mycophenolic Acid**

All patients will either continue on or initiate use of MMF (or MPA) during screening or no later than Day 1. The initial dosage will be 1500 mg/day by mouth (or equivalent), given in two or three divided doses and titrated upward to 2.0–2.5 g/day (or equivalent) in divided doses by Week 4. The dose may be increased by 500 mg/wk (or equivalent), as tolerated up to a maximum dosage of 2.5 g/day (or equivalent). Reductions, as outlined in [Appendix 4](#), will be allowed because of adverse effects. Investigators, at their discretion, may use MPA as a substitute for MMF, with a 360-mg dose being equivalent to a 500-mg dose of MMF.

Based on randomized controlled clinical studies, approximately 30–40% of patients with LN may achieve a CRR with initial therapy with either cyclophosphamide or MMF in combination with corticosteroids (Dall'Era et al. 2011). In this group, the benefit of added therapy may be minimal, and the risks of added therapy may be unwarranted. The investigator should assess whether eligible patients may benefit from an initial trial of standard-of-care therapy prior to enrollment into the study.

For those patients who enter the study already receiving a dosage of MMF (or MPA) higher than 1500 mg/day (or equivalent), MMF (or MPA) will be titrated upward, as tolerated, to a goal of 2.5 g/day (or equivalent), given in divided doses, by Week 4. A patient's current dose of MMF (or equivalent) will be given in two or three divided doses and will be increased by 500 mg/wk (or equivalent) as tolerated. Refer to [Appendix 4](#) for further details.

Use of MMF (or equivalent) during pregnancy is associated with increased risks of spontaneous abortion and congenital malformations, especially external ear and other facial abnormalities, including cleft lip and palate, and anomalies of the distal limbs, heart, esophagus, kidney, and nervous system. Because of this, women of reproductive potential must be counseled regarding pregnancy prevention and planning and must use effective contraception prior to initiation of this therapy.

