- Viral hepatitis: Measurement of HBsAg, HBcAb, and hepatitis C antibody. Patients who are HBsAg negative and HBcAb positive will also be evaluated for HBV DNA.
- Pregnancy test: All women of childbearing potential (including those who have had a tubal ligation) will have a pregnancy test at each visit. Positive test results will be confirmed with a serum pregnancy test. The infusion must not be administered unless the pregnancy test is negative.
- Pharmacokinetics and ADA: To be measured as outlined in the schedule of assessments.

The following samples will be sent to the Sponsor or a designee for analysis:

- Cells from blood and urine for B-cell and lupus-related biomarkers, which may include but are not restricted to CD19+ B cells and mRNA associated with B-cell activity
- Serum, plasma, and urine for B-cell and lupus-related biomarkers, which may include but are not restricted to B-cell activating factor (BAFF)
- Renal biopsy slides and/or formalin-fixed paraffin-embedded blocks for immunohistopathology assessment

Any leftover material from pharmacokinetics, ADA, and biomarker samples may be used for additional assay development and assay validation purposes during the development of study- or compound-related assays and exploratory research in addition to the mentioned intended uses. These samples will be stored until the study results have been reported, with the exception of some blood, tissue, and urine samples that might be stored for 5 years after all study data have been collected. For patients who agree to take part in optional long-term storage at Roche Clinical Repository (RCR), unused blood, urine, and kidney biopsy samples will be stored and destroyed no later than 15 years after the date of final closure of the associated clinical database.

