#### **5.4.3           Reporting Requirements for Pregnancies**

##### **5.4.3.1       Pregnancies in Female Patients**

Female patients of childbearing potential will be instructed to immediately inform the investigator if they become pregnant during the study or within 18 months after the last dose of study drug. A Clinical Trial Pregnancy Reporting Form should be completed by the investigator immediately (i.e., no more than 24 hours after learning of the pregnancy) and submitted either by faxing or by scanning and emailing the form using the fax

number or email address provided to investigators. Pregnancy should not be recorded on the Adverse Event eCRF. The investigator should discontinue study drug and counsel the patient, discussing the risks of the pregnancy and the possible effects on the fetus. Monitoring of the patient should continue until conclusion of the pregnancy. Any serious adverse events associated with the pregnancy (e.g., an event in the fetus, an event in the mother during or after the pregnancy, or a congenital anomaly/birth defect in the child) should be reported on the Adverse Event eCRF. In addition, the investigator will submit a Clinical Trial Pregnancy Reporting Form when updated information on the course and outcome of the pregnancy becomes available.

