#### **5.4.3.2      Pregnancies in Female Partners of Male Patients**

Male patients will be instructed through the Informed Consent Form to immediately inform the investigator if their partner becomes pregnant during the study or within 12 months after the last dose of study drug. A Clinical Trial Pregnancy Reporting Form should be completed by the investigator immediately (i.e., no more than 24 hours after learning of the pregnancy) and submitted either by faxing or by scanning and emailing the form using the fax number or email address provided to investigators. Attempts should be made to collect and report details of the course and outcome of any pregnancy in the partner of a male patient exposed to study drug. To allow the Sponsor to collect additional information, the Sponsor will request that the pregnant partner signs an Authorization for Use and Disclosure of Pregnancy Health Information to allow for follow-up on her pregnancy. If the authorization has been signed, the investigator will update a Clinical Trial Pregnancy Reporting Form with additional information on the course and outcome of the pregnancy. An investigator who is contacted by the male patient or his pregnant partner may provide information on the risks of the pregnancy and the possible effects on the fetus, to support an informed decision in cooperation with the treating physician and/or obstetrician.

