2.2.4 Safety Outcome Measures

The safety outcome measures are as follows:

- Incidence, type, and severity of adverse events (AEs) and adverse events of special interest (AESI), including infusion reactions, infections, thrombocytopenia, and neutropenia
- Proportion of patients with abnormal vital signs
- Proportion of patients with abnormal laboratory values

Safety will be monitored through regular physical examinations, vital signs, hematologic and chemistry laboratory tests, urinalyses, and incidence and severity of AEs.

In addition, the following will be examined:

- Circulating B cells, T cells, neutrophils, and other cell populations
- Plasma immunoglobulins (total immunoglobulin [Ig], immunoglobulin G [IgG], immunoglobulin M [IgM], and immunoglobulin A [IgA])
- Pregnancy
- Antibody titers for mumps, rubella, varicella, tetanus, influenza, and *Streptococcus pneumoniae*

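### The SAP's pregnancy listing draws only on serum tests, so it omits partner pregnancies, some form-reported patient pregnancies, and all pregnancy outcomes

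*SAP*

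**What the plan says.** SAP 2.2.4 introduces a group of safety items with "In addition, the following will be examined", and pregnancy is one of them; protocol 3.4.2 does the same. The only method the SAP then gives is in 4.8.2: "Positive pregnancy results will be listed, as identified using the serum test results". The SAP does not mention the pregnancy form.

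The protocol sets up the collection in 5.4.3. Female patients are to tell the investigator "if they become pregnant during the study or within 18 months after the last dose of study drug" (5.4.3.1), and male patients "if their partner becomes pregnant during the study or within 12 months after the last dose of study drug" (5.4.3.2). In both cases the investigator completes a Clinical Trial Pregnancy Reporting Form within 24 hours and updates it with course and outcome, for partners subject to a signed authorization. Section 5.4.3.1 adds: "Pregnancy should not be recorded on the Adverse Event eCRF". For partners, 5.4.3.2 says: "Attempts should be made to collect and report details of the course and outcome of any pregnancy in the partner of a male patient" who was exposed to study drug. Section 5.5.1 requires pregnancies reported during the study to be followed to outcome.

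Testing is confined to patients: "All women of childbearing potential (including those who have had a tubal ligation) will have a pregnancy test at each visit" (4.5.8), with serum confirmation of any positive result. At Weeks 76 and 104 the test is a urine test, with central serum testing only if it is positive (Appendix 2).

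**The concern.** The source named in the SAP is not the source the protocol built for this outcome. A listing restricted to serum results leaves out pregnancies that the form exists to capture, and the adverse event tables cannot restore them, because a pregnancy as such is barred from the adverse event eCRF.

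The setting makes a full account worth having. Protocol 1.1 describes SLE as mainly a disease of women of childbearing age. Mycophenolate is background therapy, and protocol 4.3.2.2 warns: "Use of MMF (or equivalent) during pregnancy is associated with increased risks of spontaneous abortion and congenital malformations". After Week 52 it may be reduced, replaced or withdrawn (4.4.1.2), so exposure around conception will differ between patients. At stake is whether a reader of the final report can set the reported abortions and birth defects against all known pregnancies in each arm.

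**Working it through.** The plan states no figure here, so the check is a comparison of text plus arithmetic on visit days.

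**1. Which pregnancies reach which output**

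| Case | Pregnancy form | Serum listing (SAP 4.8.2) | SAE output (SAP 4.8.2) |
|---|---|---|---|
| Patient, positive at a study visit | Yes | Yes, through serum confirmation; outcome not shown | Only if there is an SAE |
| Patient, reported with no study serum sample | Yes | No | Only if there is an SAE |
| Partner of a male patient | Yes | No; partners are not tested | Abortion or birth defect (protocol 5.4.3.3, 5.4.3.4) |

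The partner omission is complete by construction. The patient omission depends on how often a form arrives without a serum sample.

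**2. How large the patient gap can be**

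The widest intervals between scheduled tests (Appendices 1 and 2) are:

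- Day 252 to 364: 364 − 252 = 112 days (16 weeks)
- Day 364 to 532: 532 − 364 = 168 days (24 weeks)
- Day 532 to 728: 728 − 532 = 196 days (28 weeks)

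A full-term pregnancy does not fit inside 28 weeks. In a woman who attends every visit, it meets a test unless it begins too close to her last one. A pregnancy that starts and ends between two tests will usually be a loss or termination, which 5.4.3.3 makes an SAE. The uncovered patients are therefore mainly those who no longer attend visits and those who conceive close to their last test.

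**3. Whether the form window outlasts testing**

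For a patient last dosed on Day 182, taking 18 months as 548 days, the window closes at 182 + 548 = Day 730, against the Week 104 test on Day 728. The window and the testing schedule end almost together, so the window itself adds little for patients who attend throughout.

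**4. How many partners are involved**

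The sex split of the trial is not given. Protocol 1.1 puts the adult ratio at about nine women to one man. If the trial follows it, 120 × 1/10 = 12 patients are men; half or twice that share gives 6 or 24. This counts men, not pregnancies, and the documents give no pregnancy rate.

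**The case against.** **Patients are mostly covered.** Every positive visit test is confirmed in serum, so the planned listing should hold most patient pregnancies. This stands. A reader might infer that there is no list of pregnancies and no denominator at all; that is too strong, because there is a list and it is incomplete.

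**Serious outcomes are captured elsewhere.** Abortions and birth defects, including defects in a partner's child, go on the adverse event eCRF (5.4.3.3, 5.4.3.4), as do other SAEs associated with a patient's pregnancy (5.4.3.1). The SAP summarizes or lists SAEs, and its listings show all adverse events reported. This stands too. The documents do not support a reading that teratogenic outcomes go unreported. One caution: 5.3.1 and 5.4.2.2 give different reporting periods after the last dose (Week 104 or 76 weeks, whichever is longer, against 52 weeks) and need reconciling, although 5.4.3.3 and 5.4.3.4 carry no time limit of their own.

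**The mycophenolate warning is about maternal use.** It cannot be carried over to partners, the one group wholly missed. Nor can every patient be assumed to be taking it after Week 52. It supports recording exposure for patients and goes no further.

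**The report may hold more than the SAP plans.** The sponsor receives and follows up each pregnancy (5.4.3, 5.5.2), this SAP covers only the final report, and the Week 52 and Week 104 reports already exist. A reader might infer that the final report will under-report pregnancies, but that cannot be shown from these documents. What can be shown is that the SAP plans no output from the forms.

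**The change is more than a sentence.** Forms are faxed or emailed, the SAP reports from the final locked database (SAP 1, 4.4), partners are outside the safety population (SAP 4.1.3), and partner follow-up needs authorization. This stands in part: it limits how complete the partner rows can be, but it is no reason to omit them.

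**Conclusion.** The point holds as a matter of listing completeness. SAP 4.8.2 names a source that cannot yield any partner pregnancy, misses patient pregnancies known only from the form, and carries no outcome for those it does include. The loss is total for partners of a probably small number of men (about 12 under the stated assumption) and should be small for female patients, provided visits are attended and serum confirmation is done as required. What is missing is a full list of pregnancies, including normal and unknown outcomes, beside which the reported SAEs can be read. The number of missed pregnancies cannot be estimated from the documents. The point is minor: the primary and secondary analyses, error rates and sample size are untouched.

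**What to change.** Replace the SAP 4.8.2 sentence with a rule on these lines: all pregnancies in patients and, separately, in partners of male patients, identified from the Clinical Trial Pregnancy Reporting Form or a positive serum test, will be listed by treatment arm with outcome (including unknown) and, for patients, study-drug and MMF/MPA exposure around conception where available. Show one entry per pregnancy, and state how the form data will be brought into or reconciled with the locked database.

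The protocol already requires the reports and their follow-up, so no new visit, test or clinical rule is needed. The cost is one reconciliation of forms with laboratory data and one revised listing. Some partner outcomes may stay missing where authorization is not given, and the listing should mark them as such.
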